4.2.2 Immunogenicity

Not applicable

4.2.3 Efficacy

Not applicable

4.2.4 Derived Other Variables

4.2.4.1 Age for Demographics

The age of a subject in the study was the calendar age in day at the time of inclusion.

4.2.4.2 Subject Duration

The duration of a subject in the study until last visit is computed as follows:

Maximum (Date of last visit, Date of term form) – (Date of V01) +1.

The duration of a subject in the study including follow-up is computed as follows:

Maximum (Date of last visit, Date of term form, Date of last follow-up contact) – (Date of V01) +1.

4.2.4.3 Duration of the Study

The duration of the study until last visit is computed as follows:

Maximum of all subjects (Date of last visit, Date of termination form) – minimum for all subjects (Date of V01) +1.

The duration of the study including follow-up is computed as follows:

Maximum of all subjects (Date of last visit, Date of termination form, Date of last follow-up contact) – minimum for all subjects (Date of V01) +1

5 Statistical Methods and Determination of Sample Size

The statistical analyses will be performed under the responsibility of the Sponsor's Biostatistics platform using SAS® Version 9.4 software or later. The results of the statistical analysis will be available in the final clinical study report (CSR).

For descriptive purposes, the following statistics in Table 5.1 will be presented. The confidence interval (CI) for the single proportion will be calculated using the exact binomial method (Clopper-Pearson method, quoted by Newcombe (7)).

Table 5.1: Descriptive statistics produced

Baseline characteristics and	Categorical data	Number of subjects. Percentage of subjects.
follow-up description Continuous data	Mean, standard deviation, quartiles, minimum, and maximum.	
Clinical safety results	Categorical data	Solicited: Number and percentage (95% CIs) of subjects. Unsolicited: Number and percentage (95% CIs) of subjects, and number of events.

5.1 Statistical Methods

5.1.1 Hypotheses and Statistical Methods for the Objectives

5.1.1.1 Hypotheses

No hypotheses will be tested. Descriptive statistics will be presented.

5.1.1.2 Statistical Methods

5.1.1.2.1 Safety

Safety analysis will include but not be limited to the following:

- The number and percentage of subjects reporting any solicited injection site reactions and solicited systemic reactions occurring from D0 to D07 after each vaccination will be summarized by study group for intensity, time of onset period, days of occurrence, and action taken.
- Immediate unsolicited systemic AEs and unsolicited AEs occurring up to D30 after each vaccination will be summarized.
- The number and percentage of subjects reporting any unsolicited non-serious AEs will be summarized by study group, intensity, time of onset period, duration, and by MedDRA preferred term and system organ class (SOC), as well as by relationship to the study vaccine.
- The number and percentage of subjects reporting at least one of any MAAEs will be summarized throughout the trial.
- The number and percentage of subjects reporting at least one of any SAEs will be summarized by study group, seriousness criterion, outcome, and by MedDRA preferred term and SOC, as well as by relationship to the study vaccine.
- The number and percentage of subjects reporting at least one of any AESIs will be summarized throughout the trial.

Safety results will be described for subjects in all study groups. The main parameters (e.g. percentage) for the safety endpoints will be described by 95% CIs using the exact binomial method (Clopper-Pearson method) (7).

Analyses will contain at least the descriptions listed in

Table 5.2

Table 5.2: Statistical analyses for safety observational objective

Safety Events	Time and Group	Description
Immediate unsolicited non- serious systemic AE	Within 30 minutes after each vaccination in Group1 and Group 2;	Percentage of subjects that have the event, MedDRA terms, intensity, relationship, study discontinuation, duration
Solicited injection site reactions	D0 to D7 after each vaccination in Group1 and Group 2;	Percentage of subjects that have the event, time of onset, duration, intensity, action taken, study discontinuation, number of days of occurrence, temperature collection routes
Solicited systemic reactions		
Unsolicited non- serious AE/AR	D0 to D30 after each vaccination in Group1 and Group 2;	Percentage of subjects that have the event, MedDRA terms, time of onset, duration, intensity, relationship, action taken, study discontinuation
AEs leading to study discontinuation	D0 to D30 after each vaccination in Group 1 and Group 2; D31 to next visit after each vaccination in Group1 and Group 2; During the whole study in Group 1 and Group 2	Percentage of subjects that have the event, MedDRA terms, time of onset, duration, intensity, relationship, action taken, outcome, study discontinuation
SAE (including AESI)	D0 to D7 after each vaccination in Group1 and Group 2; D0 to D30 after each vaccination in Group1 and Group 2; D31 to next visit after each vaccination in Group1 and Group 2; During the whole study in Group1 and Group 2	Percentage of subjects that have the event, MedDRA terms, time of onset, duration, relationship, seriousness criteria, outcome, study discontinuation
MAAE	D0 to D30 after each vaccination in Group 1 and Group 2; D31 to next visit after each vaccination in Group1 and Group 2; During the whole study in Group 1 and Group 2	Percentage of subjects that have the event, MedDRA terms, time of onset, duration, intensity, relationship, action taken, outcome, study discontinuation

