	• SAEs (including AESIs) and MAAEs will be recorded throughout the study. The subject's parent / guardian will record information in a diary card about SAEs and MAAEs from Visit 1 to Visit 2, from Visit 2 to Visit 3, from Visit 3 to Visit 4, and from Visit 4 to Visit 5. SAEs and MAAEs will also be recorded in a memory aid from D31 after the last vaccination visit until the 6-month follow up phone call.
	• The subject's parent/ guardian will be asked to notify the site immediately about any potential SAEs at any time during the trial.
	• Staff will contact the subjects' parent/ guardian by telephone 8 days (+2 days) after each vaccination visit to identify the occurrence of any SAEs (including AESIs) not yet reported and to remind them to complete the diary card after each vaccination visit and to bring it back at the subsequent visit.
	• The completed diary cards will each be collected and reviewed with the subject's parent/ guardian at the subsequent visit.
	• Staff will contact the subjects' parent/ guardian by telephone within 14 days before Visit 4 to remind them about the forthcoming study visit. If the subject's participation in the study is discontinued, the information recorded on the diary card will be reviewed at this time and the subject's parent / guardian will be asked to mail the diary card to the site.
	• Staff will contact the subjects' parent/ guardian by telephone at 6 months (+30 days) after the last vaccination visit to review the memory aid and identify the occurrence of any MAAEs, as well as SAEs (including AESIs) that have not been reported.
Duration of Participation in the Trial:	The duration of each subject's participation in the trial will be approximately 16 months, which will include a safety follow-up contact at 6 months after the final vaccination.
Investigational Product:	MenACYW conjugate vaccine : Meningococcal Polysaccharide (Serogroups A, C, Y, and W) Tetanus Toxoid Conjugate Vaccine (Sanofi Pasteur Inc., Swiftwater, PA, USA)
Form:	Liquid solution
Composition:	Each 0.5 milliliter (mL) dose of MenACYW conjugate vaccine is formulated in sodium acetate buffered saline solution to contain the following ingredients:
	Meningococcal capsular polysaccharides:
	Serogroup A
	Tetanus toxoid protein carrier approximately 55 µg*
	* Tetanus toxoid protein quantity is approximate and dependent on the polysaccharide-to-protein ratio for the conjugates used in each formulation.
Route:	Intramuscular (IM)

Batch Number:	To be determined

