1.2.1.1 Study MET39 (Phase II)

MET39 was a Phase II, randomized, open-label, multi-center study conducted in the US for which 580 healthy subjects from 2 to 15 months of age were enrolled. This study evaluated the optimal vaccination schedule in the infant/toddler population. Subjects in Group 1 through Group 4 received 1, 2, or 3 primary doses plus an additional dose of the MenACYW conjugate

vaccine in the second year of life, concomitantly with routine pediatric vaccines at several different vaccination schedules. Subjects in Group 5 received 1 dose of the MenACYW conjugate vaccine concomitantly with routine pediatric vaccines. The routine pediatric vaccines given concomitantly with MenACYW conjugate vaccine at various schedules included PREVNAR[®] (pneumococcal conjugate vaccine) or PREVNAR 13[®] (pneumococcal 13-valent conjugate vaccine [PCV13]), Pentacel[®] (diphtheria, tetanus, pertussis [acellular, component]-poliovirus [inactivated]//*Haemophilus influenzae* type b [dTaP-IPV//Hib]), ROTARIX[®] (monovalent rotavirus vaccine [RV1]) or RotaTeq[®] (pentavalent rotavirus vaccine[RV5]), hepatitis B vaccine, M-M-R[®] II vaccine (measles, mumps, and rubella vaccine [MMR]), and VARIVAX[®] (varicella vaccine).

Immunogenicity

After the primary series consisting of 1, 2, or 3 doses of MenACYW conjugate vaccine, protective serum bactericidal assay using human complement (hSBA) threshold titers of \geq 1:8 were attained by > 88% of subjects for serogroup C and by 62% to 74% for serogroup A. For serogroups Y and W, \geq 90% achieved the threshold titer after 3 doses, 75% to 84% after 2 doses, but only 25% after a single dose administered at 6 months of age.

After an additional dose of MenACYW conjugate vaccine in the second year of life (12 or 15 months of age), between 91% and 100% of the subjects achieved the protective threshold regardless of the number of doses they received in the first year of life.

Safety

MenACYW conjugate vaccine was well tolerated in infants and toddlers regardless of the immunization schedule and the number of doses administered. Safety results were comparable to those seen in control group subjects regardless of the immunization schedule and the number of doses administered. The safety profile of the licensed vaccines given concomitantly with MenACYW conjugate vaccine was similar to that of the licensed vaccines given concomitantly without MenACYW conjugate vaccine.

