5.1.2 Justification of the Study Design

The MET41 study is part of an ongoing development program that focuses on demonstrating that the safety profile of the MenACYW conjugate vaccine is acceptable and not different from that of licensed quadrivalent meningococcal conjugate vaccines, and that the immunogenicity of the MenACYW conjugate vaccine is non-inferior to licensed comparators in direct comparison trials. MET41 is a pivotal Phase III safety study in which the vaccine candidate will be evaluated in infants/toddlers receiving concomitantly licensed routine pediatric vaccines in the US. This study is designed to describe the safety profile following a 4-dose series of the MenACYW conjugate vaccine or the licensed comparator MENVEO[®] in this population. Enrollment in the study will start at 6 to 8 weeks of age.

The concomitant administration of standard of care pediatric vaccines together with 5 different administration schedules of the MenACYW conjugate vaccine has been assessed in infants/toddlers 2 to 15 months of age in the US in the MET39 study. The subjects received during, or prior to the study, a number of licensed recommended vaccines at 2, 4, and 6 months of age: Pentacel[®], either Prevnar[®] or Prevnar 13[®], RotaTeq[®] or ROTARIX[®], and ENGERIX-B[®] or RECOMBIVAX HB[®]. All subjects received M-M-R[®] II and VARIVAX[®] at 12 months of age. A total of 457 subjects completed the study. The immunogenicity and safety profiles of selected licensed pediatric vaccines (Pentacel[®], Prevnar[®] or Prevnar 13[®], M-M-R[®] II, and VARIVAX[®]) were assessed when administered either concomitantly with or without MenACYW conjugate vaccine. There was no evidence of interference with the pediatric routine vaccines administered concomitantly with MenACYW conjugate vaccine and the vaccine was safe and well tolerated regardless of the number of doses administered during the first year of life.

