6.5 Randomization and Allocation Procedures

On the day of enrollment, subjects who meet the inclusion/exclusion criteria and whose parent / guardian signs the ICF will be randomly assigned to Group 1 or Group 2 in a 3:1 ratio such that Group 1 will have approximately 2310 subjects and Group 2 will have approximately 770 subjects.

Site staff will connect to the IRT system, enter the identification and security information, and confirm a minimal amount of data in response to IRT system prompts. The IRT system will then provide the vaccine assignment and subject number. The full detailed procedures for group allocation are described in the Operating Guidelines. If the subject is not eligible to participate in the study, then the information will only be recorded on the subject recruitment log.

Subject numbers that are assigned by the IRT system will consist of a 12-digit string (a 3-digit country identifier, a 4-digit study center identifier, and a 5-digit subject identifier). For example, Subject 840000100005 is the fifth subject enrolled in Center Number 1 in the US (840 being the US country code).

Subject numbers should not be reassigned for any reason. The randomization codes will be kept securely in the IRT system.

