4.2.1.3 SAEs (including AESIs)

An event will be considered as a serious event if "Yes" is checked for "Serious" in the CRF.

An event will be considered as an AESI if "Yes" is checked for "Is the event an AESI?" in the CRF.

SAEs (including AESIs) will be analyzed throughout the study using the following periods:

- Within 7 days after vaccination
- Within 30 days after vaccination
- During the study (i.e., all SAEs occurred during the study), including the 6-month follow-up period

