5.2.1.1 Overall Safety Analysis Set for Any Dose

The overall SafAS is defined as those subjects who have received at least one dose of the study vaccines and have any safety data available. All subjects will have their safety analyzed after any dose according to the vaccine received at the first dose.

Safety data recorded for a vaccine received out of the protocol design will be excluded from the analysis (and listed separately).

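### Whole-study SAE, AESI and MAAE percentages take no account of follow-up time, so they run low if read as 16-month risk; a follow-up-adjusted estimate would be a cheap improvement.

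*SAP*

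**What the plan says.** The SAE (including AESI) and MAAE rows of SAP Table 5.2 (section 5.1.1.2.1) each include the period "During the whole study in Group 1 and Group 2". The summary is the percentage of subjects with the event, with a Clopper-Pearson 95% interval. SAP 4.2.1.3 defines the SAE period as "During the study (i.e., all SAEs occurred during the study), including the 6-month follow-up period", and SAP 4.2.1.4 does the same for MAAEs. The protocol synopsis gives the length: "The duration of each subject's participation in the trial will be approximately 16 months".

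The denominator comes from SAP 5.2.1.1: "The overall SafAS is defined as those subjects who have received at least one dose of the study vaccines and have any safety data available". It sets no minimum follow-up. The rule in SAP 4.2.1.1.3 that drops subjects without usable data applies to solicited reactions only.

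SAP 4.2.4.2 does derive follow-up time ("The duration of a subject in the study including follow-up is computed as follows"), but no planned safety output uses it. Neither document has a censoring rule, a person-time rate, a cumulative incidence or an assumed dropout rate. SAP 5.3.1 states that nothing is replaced.

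Protocol 5.2.11 limits the loss. Sites complete safety follow-up after termination for an AE, a protocol deviation or loss of eligibility. They attempt the 6-month contact after withdrawal by the parent unless contact has been refused. They seek nothing further for subjects lost to follow-up or for no-contact withdrawals.

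**The concern.** A simple percentage equals the 16-month risk only if everyone is observed for 16 months or has the event first. A subject who disappears after the first dose without an event stays in the denominator and adds nothing to the numerator, whatever happens later. Events missed in this way can only lower the percentage. The exact interval allows for sampling error, not for unseen time.

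The trial's only objective is to describe safety. SAP section 1 also speaks of showing that the profile is similar to that of the comparator. If unrecovered loss differs between groups, two equal risks would give different percentages.

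**Working it through.** **Inputs from the documents.** Group sizes: "Group 1 will have approximately 2310 subjects and Group 2 will have approximately 770 subjects" (Protocol 6.5). Follow-up is about 16 months. Intervals are Clopper-Pearson, 95%, two-sided. The plan gives no figure for loss or for SAE, AESI or MAAE frequency, so there is no plan figure to reproduce.

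**Assumed inputs.** Whole-study risk P of 50% (a common MAAE-type outcome), 5% (SAE-type) or 0.2% (AESI-type). Unrecovered loss d of 5%, 10% or 21.2%. The last value is borrowed from the only attrition figures in the documents, those of the Phase II infant study MET39: "580 healthy subjects from 2 to 15 months of age were enrolled" (Protocol 1.2.1.1) and "A total of 457 subjects completed the study" (Protocol 5.1.2), so 1 - 457/580 = 0.212.

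**Formula.** With a constant hazard, let L = -ln(1-P). A subject lost at a time uniform over follow-up has, on average, an observed risk of 1 - (1-e^-L)/L = 1 - P/L. The expected crude percentage is (1-d)P + d(1 - P/L).

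For P = 50%: L = 0.6931 and 1 - 0.5/0.6931 = 0.2787.
- d = 5%: 0.95 x 0.5 + 0.05 x 0.2787 = 0.489
- d = 10%: 0.90 x 0.5 + 0.10 x 0.2787 = 0.478
- d = 21.2%: 0.788 x 0.5 + 0.212 x 0.2787 = 0.453

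For P = 5%: L = 0.0513 and the average observed risk of a lost subject is 0.0252.
- d = 10%: 0.0450 + 0.0025 = 0.0475
- d = 21.2%: 0.0394 + 0.0053 = 0.0447

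**Results.** The interval is for Group 1 at the expected percentage. Coverage is the exact chance that the interval contains P, Group 1 / Group 2.

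| True risk | Loss | Reads | 95% CI, n = 2310 | Coverage |
|---|---|---|---|---|
| 50% | 5% | 48.9% | 46.8 to 50.9 | 81.8% / 91.0% |
| 50% | 10% | 47.8% | 45.7 to 49.9 | 44.0% / 77.4% |
| 50% | 21.2% | 45.3% | 43.3 to 47.4 | 0.5% / 26.6% |
| 5% | 10% | 4.75% | 3.9 to 5.7 | 92.9% / 95.3% |
| 5% | 21.2% | 4.5% | 3.7 to 5.4 | 81.2% / 91.9% |
| 0.2% | 21.2% | 0.18% | about 0.05 to 0.45 | 97.4% / 98.7% |

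With no loss, coverage is at least 95% throughout.

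**Sensitivity at 21.2% loss and 5% risk.** If all loss falls in the first 4 months, the percentage reads 4.1% and coverage is 47.8% / 81.1%. If it all falls in months 10 to 16, the percentage reads 4.8% and coverage is 94.1% / 95.7%. If half of these subjects are recovered at the 6-month call, it reads 4.7% and coverage is 92.6% / 95.2%.

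**Between groups.** With a true 50% risk in both groups and loss of 10% in one and 21.2% in the other, the gap is 47.8 - 45.3 = 2.5 percentage points. With 16% and 21% it is 46.5 - 45.4 = 1.1 points. At 5% risk, 16% against 21% gives 4.60 - 4.48 = 0.12 points.

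**Check of the remedy.** In 2000 simulated trials with 21.2% uniform loss, Kaplan-Meier with a log-log interval gave these results in Group 1: mean 50.0% and coverage 95.4% for a true 50%, and mean 5.01% and coverage 95.0% for a true 5%. Group 2 gave 50.1% (95.1%) and 5.03% (95.0%). The person-time rate was not simulated.

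**The case against.** Several objections stand, at least in part.

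- **Most discontinuations need not be lost to safety.** It would be wrong to infer that every early dropout counts as fully followed without being so. Protocol 5.2.11 keeps AE, protocol-deviation and eligibility terminations in follow-up and tries to reach parents who withdrew. The bias comes only from subjects lost to follow-up, no-contact withdrawals and those not reached at the 6-month call.
- **The 21% is not this trial's loss.** It is non-completion in an open-label, five-group Phase II study with other schedules. Nor does the SAP predict COVID-19 losses. Section 5.1.1.2.2.3 provides for summarising any impact, with subset summaries if more than 10% of subjects are affected.
- **The percentage is a correct description** of vaccinated subjects with a reported event. It is biased only as a 16-month risk, and the SAP does not call it one.
- **Other outputs suffer less.** The windows after each vaccination and the dose-specific sets SafAS1 to SafAS4 are little affected by later loss. They do not add up to a whole-study risk, however. The 4-dose set selects subjects who stayed long enough to receive every dose.
- **The list of analyses is open-ended** (SAP 5.1.1.2.1), so an adjusted estimate is allowed. Nothing commits to one.

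**Conclusion.** The whole-study percentages are low as estimates of 16-month risk whenever some subjects are lost to safety follow-up. That direction is certain. The size is not, because it rests on assumed risks, a constant hazard, evenly spread unrecovered loss and a loss rate that the documents do not give. Under those assumptions the effect matters for common MAAEs: about 2 points at 10% loss and nearly 5 at 21%, with Group 1 intervals that exclude the true 50%. At 5% loss the interval still contains it.

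A reader might infer that the intervals fail for all three outcomes. They do not. At a 5% SAE risk the expected intervals contain 5%, although repeated-sample coverage in Group 1 falls to about 93% at 10% loss and 81% at 21%. At a 0.2% AESI risk the estimate is slightly low, but coverage stayed at 95.8% or more in every scenario examined, up to 35% loss.

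A reader might also take the SAP 5.5 detection statement as a hidden allowance for heavy loss. The formula 1-(1-p)^n gives 99.0% for both stated cases, against the stated 95% or so, and about 35% non-evaluable subjects would bring it to 95%. The documents state no such allowance, so this is no evidence of expected dropout.

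This is a cheap improvement to a descriptive analysis, not an error that invalidates it.

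**What to change.** Keep every planned percentage. For the whole-study SAE, AESI and MAAE rows of Table 5.2, add by group one of the following:

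- Kaplan-Meier cumulative incidence at the end of follow-up, with a 95% CI; or
- subjects with a first event per 100 person-years, with an exact Poisson 95% CI.

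In either case, end each subject's time at the first event or the last actual safety contact. Do not use the SAP 4.2.4.2 duration as it stands. It takes the latest of several dates including the termination form, and for a lost subject that form can be completed after the location efforts of Protocol 5.2.9 and 5.2.10, well after the last safety contact. State the number followed to the 6-month call by group.

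A rule is also needed for first events with a missing start date, which SAP 5.3.1.5 leaves unimputed. SAP 4.2.1.2.4 already treats such unsolicited AEs as occurring just after the assigned vaccination, and the same convention would serve.

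The cost is slightly more output and no new data collection. The person-time rate assumes a roughly constant hazard from 2 to 18 months of age. Kaplan-Meier does not, and would be my choice. Both assume that loss is unrelated to later event risk.
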